4.5. Appendix Form

4.5.1. List of occurrence of malfunctions and infectious diseases

Prepare a list of the occurrence of malfunctions and infectious diseases.

List of Incidence of Failure/Infectious Diseases (Annual Report: Form 3 Re-Examination: Form 2)

- Analysis set: Stent implantation cases

Line

No	Item name	Definition Content
1	Number of facilities surveyed	Use the same site as a single institution
2	Number of subjects surveyed	Tabulate the number of patients surveyed
3	Number of patients with malfunctions	If more than one malfunction etc. occurs in the same patient, the data will be summarized as 1 subject.
4	Number of incidents of failure, etc.	Aggregate the number of incidents of failure, etc.
5	Incidence of failure	= number of cases with malfunctions, etc. $\times 100$ number of cases to be investigated.
6	Event name	Aggregate using MedDRA coding

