1.3. Estimated number of registrations

This survey aims to enroll approximately 300 patients at approximately 30 institutions.

Previous studies predicted a 1-year MACE (Combined Assessment of Cardiac Death, Myocardial Infarction and Ischemic Target-Lesion Revascularization) of 15% in this survey. When 300 patients were enrolled, 1/2 of the 95% two-sided confidence interval for an MACE rate of 15% was 4.2%, corresponding to 28% of the expected MACE rate of 15%. Within this range, the efficacy and safety of

the device can be sufficiently assured in the real-world clinical setting in Japan.

A total of 62 subjects continued to participate in the clinical study described above.

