2.1. Analysis population definitions

No	Definition name	Definition Content
1	Survey period	March 7, 2013 - December 31, 2019
2	Date of data lock (snapshot)	Data lock (snapshot) dates for annual reports are as follows 1st: September 5, 2013 2nd: September 5, 2014 3rd: September 5, 2015 4th: September 5, 2016 5th: September 5, 2017 6th: September 5, 2018 7th: September 5, 2019 Reexamination: September 5, 2019 Subjects with fixed CRFs by the time of data lock.
3	CRF-collected subjects	Subjects whose CRFs were fixed
4	Subjects who are out of the survey	The cases who were treated with out-of survey stent, among CRF-collected subjects in newly enrolled patients.
5	Subjects to be investigated	The cases excluding subjects who are out of the survey among CRF-collected subjects.
6	Non-stent implanted subjects	Among the subjects studied, the cases in which the stent to be investigated could not be placed.
7	Stenting subjects	Among the investigated subjects in newly enrolled patients, the cases who were treated with investigated stent Investigated subjects transitioning from the pre-market study.
8	Newly enrolled patients	Patients enrolled for the first time in this survey.
9	Patients transitioning from the study	Patients who participated in the Clinical Assessment of AVJ-09-385 Coronary Stenting in Japanese Subjects in AVJ-09-385 Coronary Stenting Trial.

No	Definition name	Definition Content

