4.1.1. Number of patients at each center

The number of patients collected by questionnaire, the number of patients not covered by the survey, the number of patients surveyed, the number of patients not stented, and the number of patients stented will be tabulated. In addition, the corresponding case number is indicated for cases not covered by the survey and cases not covered by the stent.

Figure 1. Case structure

- Analysis set: Cases collected by questionnaire

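### SAP 4.5.1 names two populations for the malfunction incidence, and following its header would leave out deficiencies in patients whose stent could not be implanted

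*SAP*

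**What the plan says.** SAP 4.5.1 defines the form for malfunctions and infectious diseases (Form 3 in the annual reports, Form 2 at re-examination). Its header reads "Analysis set: Stent implantation cases". Within the form, line 2 says "Tabulate the number of patients surveyed" and line 5 divides the patients with malfunctions by the "number of cases to be investigated". Line 3, the numerator, names no population.

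SAP 2.1 separates these sets:

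- Definition 5, subjects to be investigated: "The cases excluding subjects who are out of the survey among CRF-collected subjects".
- Definition 6, non-stent implanted subjects: "Among the subjects studied, the cases in which the stent to be investigated could not be placed".
- Definition 7, stenting subjects: newly enrolled investigated subjects treated with the stent, plus "Investigated subjects transitioning from the pre-market study".

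SAP 4.1.1 keeps the groups apart in the case structure: "the number of patients surveyed, the number of patients not stented, and the number of patients stented will be tabulated".

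Protocol 2.2 makes registration mandatory for a patient in whom XIENCE PRIME SV was tried but none was implanted, and asks for that patient's device deficiency information. Protocol 5.1 lists the device deficiency form among the few forms required in that case. Protocol 1 gives the frequency, type and degree of device deficiency as an objective.

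SAP 4.5.3 (serious adverse events) repeats the pattern: a stented-case header, with line 5 divided by the number of subjects surveyed.

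**The concern.** The header and the lines of one form point to different sets, and nothing says which one governs the numerator. A deficiency that prevents implantation is directly relevant to how often the device is deficient. If the header is followed, those events are collected under the protocol and then left out of the incidence built to report them.

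Failed-implant patients do appear elsewhere: by case number in SAP 4.1.1, in placement success in Table 15 (SAP 4.2.8), and in the case listing in SAP 4.7.1. None of these gives a malfunction incidence. SAP 4.5.2, which breaks the incidence down by patient background, is also limited to stented cases. The rate at stake is the one submitted each year and at re-examination.

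**Working it through.** The plan states no malfunction rate, so there is no figure to reproduce. The check has two parts: set logic, then an illustration of size.

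**Sets.** Let S be the stented patients and F the investigated patients with no XIENCE PRIME SV implanted. By definitions 5 to 7, the investigated set is N = S + F. Let mS and mF be the patients with at least one malfunction in each group. The text allows three readings:

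- A, stented cases throughout: mS / S
- B, investigated cases throughout: (mS + mF) / (S + F)
- C, header for the numerator, line 5 for the denominator: mS / (S + F)

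Readings A and C both omit mF. B minus C is mF / N, whatever mS is. If F = 0, all three agree.

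**Inputs.** SAP 1.3 plans approximately 300 new patients and adds: "A total of 62 subjects continued to participate in the clinical study described above". Definition 7 counts transition patients as stented, so N = 300 + 62 = 362. Assumptions: every CRF is fixed, no new patient is out of survey, no transition patient has a malfunction, and each failed-implant patient counted here has a deficiency (F = mF). The values of mS (3, 10, 30) and mF (1, 5, 15) are illustrative and do not come from the documents.

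**Difference B minus C.** 1/362 = 0.28 points; 5/362 = 1.38 points; 15/362 = 4.14 points.

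**Rates**, with Clopper-Pearson 95% intervals (the method in SAP 3.2) for B and C:

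| mS | mF | A | B | C |
|---|---|---|---|---|
| 3 | 1 | 3/361 = 0.83% | 4/362 = 1.10% (0.30 to 2.80) | 3/362 = 0.83% (0.17 to 2.40) |
| 3 | 5 | 3/357 = 0.84% | 8/362 = 2.21% (0.96 to 4.31) | as above |
| 3 | 15 | 3/347 = 0.86% | 18/362 = 4.97% (2.97 to 7.74) | as above |
| 10 | 1 | 10/361 = 2.77% | 11/362 = 3.04% (1.53 to 5.37) | 10/362 = 2.76% (1.33 to 5.02) |
| 10 | 5 | 10/357 = 2.80% | 15/362 = 4.14% (2.34 to 6.74) | as above |
| 10 | 15 | 10/347 = 2.88% | 25/362 = 6.91% (4.52 to 10.03) | as above |
| 30 | 1 | 30/361 = 8.31% | 31/362 = 8.56% (5.89 to 11.94) | 30/362 = 8.29% (5.66 to 11.62) |
| 30 | 5 | 30/357 = 8.40% | 35/362 = 9.67% (6.83 to 13.19) | as above |
| 30 | 15 | 30/347 = 8.65% | 45/362 = 12.43% (9.21 to 16.28) | as above |

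A and C never differ by more than 8.65 - 8.29 = 0.36 points in this grid, while B exceeds C by up to 4.14. The choice of denominator matters little. What matters is whether failed-implant deficiencies enter the numerator.

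**The case against.** Five points can be made for the plan.

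1. Definition 7 admits newly enrolled patients treated with the stent, and Protocol 2.2 uses treated to mean that the delivery system entered the body. Read literally, a failed implant could then be a stented case. But definition 6 puts these patients in a group of their own, and SAP 4.1.1 counts the two groups separately. The literal reading does not survive those two passages, though the wording is a further reason to name the set explicitly.

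2. The header could govern the whole form, with the surveyed label as a mere row title. That gives a coherent fraction (reading A), but it still omits the failed-implant deficiencies.

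3. Follow-up is not required in patients without an SV stent, so including them dilutes the rate of later malfunctions. This is true, but the dilution is the gap between A and C, which is small throughout the grid.

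4. The SAP does not say which CRF entries feed line 3, so equating a malfunction with a protocol device deficiency is an inference. This stands as a caveat. The inference is reasonable because both documents give the frequency of device defects as an aim.

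5. The counts are hypothetical, a failed implant need not involve a deficiency, and a patient with one failed and one implanted SV stent remains a stented case. All of this stands. The figure that does not depend on an assumed number of events is 0.28 points per affected patient, on 362 patients.

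**Conclusion.** The concern holds. SAP 4.5.1 names two different populations for one incidence, SAP 4.5.3 does the same, and no passage resolves which applies. Under either reading that follows the header for the numerator, deficiencies in failed-implant patients are missing from the malfunction incidence. Under the remaining reading the header is wrong.

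The actual effect cannot be sized from the documents. It is zero if no failed-implant patient has a deficiency. Otherwise each such patient shifts the rate by 0.28 points, assuming 362 investigated patients and that deficiencies are what line 3 counts. The header may be only a translation slip, and the table is descriptive, so no trial decision turns on it. It should still be corrected, because it feeds regulatory reports and bears on a stated objective.

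**What to change.** - **SAP 4.5.1:** set the analysis set to the subjects to be investigated (definition 5), say that this includes non-stent implanted subjects, and use it for header, numerator and denominator. This agrees with lines 2 and 5 as they stand.
- **SAP 4.5.3:** name one population for header, numerator and denominator. If stented cases are chosen, list stent-related events in non-implanted patients separately, since Protocol 2.2 requires them to be captured.
- **SAP 4.5.2:** keep stented newly enrolled patients and add a sentence that failed implants are excluded there.

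The cost is a wording change in two sections and one sentence in a third. Protocol 5.1 already provides the basic information, non-implant stent form and device deficiency form, so 4.5.1 needs no new data, row or column. The reported malfunction rate may be slightly less favourable.

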4.5.2. List of Incidence of Failures and Infectious Diseases by Patient Background

The number of patients, the number of patients with malfunctions and infections, and the incidence of malfunctions and infections will be calculated according to patient characteristics.

List of Incidence of Failures and Infectious Diseases by Patient Background

- Analysis set: Stent implantation cases (newly enrolled patients)

Patient characteristics: [] indicating Breakdown

No	Item name
1	Acute myocardial infarction (yes/no) [ST-segment elevation myocardial infarction, non-ST-segment elevation myocardial infarction]
2	Unstable angina pectoris (with or without) [Blanwald classification: Class I to Class III]
3	Stable angina pectoris (with or without) [CCS angina classification: Class I-IV]
4	Asymptomatic ischemia (with or without)
5	Old myocardial infarction (no evidence of ischemia) (yes/no)
6	Coronary artery stenosis (no evidence of ischemia) (yes/no)
7	Age (<75 years, ≥ 75 years)
8	Sex at birth (male, female)
9	Height (< 160cm, > 160cm, < 170cm, > 170cm)
10	Body weight (< 60kg, ≥ 60 kg, < 70kg, and ≥ 70 kg)
11	Body Mass Index (less than 18.5kg/m ² , greater than 18.5kg/m ² , less than 25kg/m ² , greater than 25kg/m ² , less than 30kg/m ² , greater than or equal to 30kg/m ² , less than 35kg/m ² , greater than or equal to 35kg/m ² , less than or equal to 40kg/m ² , greater than or equal to 40kg/m ²)
12	LVEF < 30% (< 30, > 30)
13	History of myocardial infarction (yes/no)
14	History of CABG (with or without)
15	Past PCI (Yes, No)

No	Item name
16	Family history of juvenile coronary artery disease (yes/no)
17	If you are currently smoking or quit smoking within the past month (yes/no).
18	Hypertension (yes/no) [requiring pharmacotherapy, not requiring pharmacotherapy]
19	Dyslipidemia (yes/no) [requiring pharmacotherapy, not requiring pharmacotherapy]
20	Renal failure (Kidney disease) History (yes/no) [On dialysis, end-stage renal failure (eGFR < 30 mL/min/1.73m ²), chronic kidney disease (eGFR < 60 mL/min/1.73m ²)]
21	History of stroke (yes/no)
22	History of serious bleeding (with or without)
23	History of unstable arrhythmia (present or absent)
24	Anticoagulant therapy (continuous administration, no continued administration)
25	History of diabetes mellitus (with or without) [Type 1 diabetes mellitus, Type 2 diabetes mellitus]
26	History of diabetes mellitus requiring medical care (with or without) [insulin therapy, oral antidiabetic drug therapy]

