4.1.6. Basic demographic information

Summary statistics of the basic demographic information specified below or proportions and confidence intervals of relevant cases will be calculated.

Table 5. Basic demographic information

- Analysis set: Stent implantation cases (newly enrolled patients)

Items * calculate summary statistics

No	Item name
1*	Age (years)
2	Age 75 years or older
3	Sex at birth (male, female)
4*	Height (cm)
5*	Body weight (kg)
6*	Body Mass Index (kg/ m ²)
7	Body Mass Index: Less than 18.5kg/m ² Body Mass Index: 18.5kg/m ² or more, less than 25kg/m ² Body Mass Index: 25kg/m ² or more, less than 30kg/m ² Body Mass Index: 30kg/m ² or more, less than 35kg/m ² Body Mass Index: 35kg/m ² or more, less than 40kg/m ² Body Mass Index: 40kg/m ² or higher

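### SAP 4.5.2: the height, BMI and LVEF classes are not partitions as printed, and the BMI bands disagree with Table 5

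*SAP*

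**What the plan says.** Section 4.5.2 of the SAP asks, for each background characteristic, for the number of patients, the number with malfunctions or infections, and the incidence. The analysis set is newly enrolled patients who received a stent.

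- Item 9: "Height (< 160cm, > 160cm, < 170cm, > 170cm".
- Item 12: "LVEF < 30% (< 30, > 30".
- Item 11, lower end: "less than 18.5kg/m ² , greater than 18.5kg/m ² , less than 25kg/m ² , greater than 25kg/m ²".
- Item 11, upper end: "less than or equal to 40kg/m ² , greater than or equal to 40kg/m ²".

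Two other items in the same list are built correctly: age (item 7) and body weight (item 10) both print ≥ at the lower bound of the upper classes. Table 5 in section 4.1.6 has BMI classes with the same cut-points. They start at "Body Mass Index: Less than 18.5kg/m"², and each later class includes its lower bound and excludes its upper bound.

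**The concern.** A table of counts and rates by class works only if each patient with a known value falls in exactly one class. Strict inequalities on both sides of a cut-point leave the patients at that value without a class. Closed bounds on both sides count them twice.

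The protocol's stated purpose includes observing device deficiencies, and section 4.5.2 is the only SAP table that gives malfunction incidence by patient background. If the printed rules were coded as they stand, the class totals would not match the analysis set. A reader could not tell a patient at a cut-point from one whose value is missing. The BMI counts could also differ between section 4.5.2 and Table 5 for the same patients.

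**Working it through.** The plan gives no figure on this point, so there is nothing to reproduce. The check has two parts.

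**1. Class membership.** Each printed class is treated as a logical condition, and the classes that contain each cut-point are counted. A partition gives 1 everywhere.

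| Item | Value | Classes containing it |
|---|---|---|
| Height (three classes) | 160 cm | 0 |
| Height (three classes) | 170 cm | 0 |
| LVEF | 30% | 0 |
| BMI, 4.5.2 | 18.5 | 0 |
| BMI, 4.5.2 | 25 | 0 |
| BMI, 4.5.2 | 30 and 35 | 1 each |
| BMI, 4.5.2 | 40 | 2 |
| BMI, Table 5 (control) | 18.5, 25, 30, 35, 40 | 1 each |
| Weight, 4.5.2 (control) | 60 and 70 kg | 1 each |

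Three classes is the natural reading of the height row, because the weight row below it has the same layout. If height is read as four separate conditions, 160 and 170 cm each fall in one class, but 159, 165 and 171 cm each fall in two. Neither reading is a partition.

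**2. Size of the height gap.** Inputs: n = 300, the enrolment target in SAP 1.3. The height distribution is an assumption, not a figure from the documents: normal, mean m of 158 to 165 cm, SD s of 8 to 10 cm. The documents give no recording precision, so two cases are shown.

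- Whole cm: expected number lost = 300 × Σ [Φ((c + 0.5 − m)/s) − Φ((c − 0.5 − m)/s)], summed over c = 160 and 170.
- To 0.1 cm: expected number lost = 300 × Σ 0.1 × f(c), where f is the normal density with mean m and SD s.

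| m | s | P(160), whole cm | P(170), whole cm | Lost, whole cm | Lost, 0.1 cm |
|---|---|---|---|---|---|
| 158 | 8 | 0.0483 | 0.0162 | 19.4 | 1.9 |
| 158 | 10 | 0.0391 | 0.0194 | 17.6 | 1.8 |
| 162 | 8 | 0.0483 | 0.0302 | 23.6 | 2.4 |
| 162 | 10 | 0.0391 | 0.0290 | 20.4 | 2.0 |
| 165 | 8 | 0.0410 | 0.0410 | 24.6 | 2.5 |
| 165 | 10 | 0.0352 | 0.0352 | 21.1 | 2.1 |

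That is about 18 to 25 patients (17.6/300 = 5.9% to 24.6/300 = 8.2%) in whole centimetres, and about 2 to 3 at 0.1 cm.

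**BMI and LVEF.** SAP 3.2 computes BMI from weight and height and gives no rounding rule. If BMI were rounded to one decimal, with an assumed mean of 23.5 to 24 and SD of 3.5, about 1.4% of patients (0.014 × 300 ≈ 4) would be at 18.5 or 25.0. Without rounding there would be fewer, though exact hits can occur: 64 kg at 160 cm gives 64/1.6² = 25. Under the same assumptions the expected number at exactly 40.0 is about 0.0001 of 300, so the double count is an error of definition with almost no practical effect. The documents give no LVEF distribution, so no size is given for it.

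**The case against.** **The intended rule is evident.** The SAP's English reads like a translation (numerators, for instance, are called molecules in section 3.2). Table 5 shows the BMI bands that were meant, and the age and weight rows show the house style. Item 12 is headed as LVEF below 30%, whose complement includes 30. A careful programmer would probably repair all three items unasked. This is fair, and it limits the consequence. It does not remove the defect, because a silent repair leaves output that does not follow the SAP. Loss of a ≥ sign when the PDF was read is an unlikely cause: the sign survives in items 7 and 10, and the BMI bounds are written in words.

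**The consequence is small.** This also stands. The table is a descriptive appendix. The overall malfunction incidence (section 4.5.1), the MACE rate (Table 18) and the stent thrombosis rate (Table 20) do not use these classes.

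**A stronger reading concerns the renal item.** Item 20 lists "end-stage renal failure (eGFR < 30 mL/min/1.73m ²), chronic kidney disease (eGFR < 60 mL/min/1.73m ²", and anyone below 30 is also below 60. A reader might infer double-counting, and a severity gradient that is hidden or reversed. The documents do not support that.

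- The square brackets mark a breakdown of a yes/no item, and nothing says that the parts of a breakdown are exclusive.
- The SAP uses overlapping breakdowns elsewhere. Table 19 item 2 lists ST-elevation and non-ST-elevation infarction beside Q-wave and non-Q-wave. Table 18 item 3 lists TLR, non-TLR TVR, and the two together.
- A class labelled chronic kidney disease with eGFR below 60 can be nested by intent, and the yes/no split is unaffected.
- The rate below 60 is a weighted average of the rate below 30 and the rate from 30 to below 60. If dialysis patients are handled consistently, nesting can dilute the contrast but cannot reverse it.

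Exclusive renal classes would be a preference, not a correction.

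**Conclusion.** The point holds for items 9, 11 and 12 of SAP 4.5.2. As printed, heights of exactly 160 or 170 cm, LVEF of exactly 30%, and BMI of exactly 18.5 or 25 fall in no class, and BMI of exactly 40 falls in two. The BMI bands also conflict with Table 5.

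The loss from the height classes depends on recording precision: about 2 to 3 of 300 patients at 0.1 cm, or about 18 to 25 in whole centimetres. Both ranges rest on the assumed height distribution and on literal programming of the printed rules. It would be wrong to quote only the whole-centimetre range, or to state as fact that patients will be lost.

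This is a minor wording error confined to one descriptive subgroup table. It does not extend to the renal item or to any overall rate.

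**What to change.** In SAP 4.5.2, rewrite three items so that each class includes its lower bound and excludes its upper bound:

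- Item 9, height: < 160; ≥ 160 to < 170; ≥ 170 cm.
- Item 11, BMI: the six bands of Table 5 (section 4.1.6), preferably by reference so that the two tables cannot diverge.
- Item 12, LVEF: < 30%; ≥ 30%.

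It would help to show the number with a missing value for each characteristic, so that the classes plus missing add up to the analysis set. The cost is a change of SAP wording and the matching lines of code. No new data are needed.

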4.5.3. Listing of Incidence of Serious Adverse Events

Prepare a list of serious adverse events.

Listing of Incidence of Serious Adverse Events (Form 3-2)

- Analysis set: Stent implantation cases

Line

No	Item name	Definition Content
1	Number of facilities surveyed	Use the same site as a single institution
2	Number of subjects surveyed	Tabulate the number of patients surveyed
3	Number of patients with adverse events	If more than one serious adverse event occurs in the same patient, it will be summarized as one subject.
4	The number of incidences of the adverse events	The number of serious adverse events is summarized.
5	Incidence of adverse events	= number of subjects with serious adverse events ♂ × 100 number of subjects surveyed
6	Event name	Aggregate using MedDRA coding

4.6. Quantitative coronary angiography (QCA).

4.6.1. QCA results before the procedure, immediately after the procedure, and at follow-up.

Summary statistics will be calculated for each observation period based on QCA results.

Table Q1 QCA results before the procedure, immediately after the procedure, and at follow-up

- Analysis set: Stent implantation cases (newly enrolled patients)

Items

No	Item name
1	Lesion length (mm)

No	Item name
2	Minimum lumen diameter (mm)
3	Reference vessel diameter (mm)
4	Diameter stenosis (%)

4.6.2. Acute-phase diameter gain and late-phase diameter loss

Summary statistics will be calculated for each stent, proximal, distal, and segment with respect to the acquired lumen diameter in the acute phase and the loss diameter in the distant phase.

Table Q2 Acute phase diameter gain and late phase diameter loss

- Analysis set: Stent implantation cases (newly enrolled patients)

Items	
No	Item name
1	Acute Gain (mm)
2	Late Loss (mm)
3	Net Gain

4.7.Listing of Case Summaries Subjects Subject to Drug Use Results Survey

